These results suggest that for a surprising number of participants there are differences between the absorption and clearance rates of insulin lispro and insulin aspart. What is not yet clear is whether these differences in PK would result in differences in glycemic regulation. There are many factors beyond insulin PK that influence the effectiveness of glycemic regulation, the size of the differences in PK in some of the participants have the potential to significantly influence key parameters of glycemia, such as mean glucose and % time in the hypoglycemic range. It is more likely that such differences could be detected if more of the other factors that may influence glycemic regulation are neutralized, as is the case when glycemic regulation is automated. Therefore, use of the bionic pancreas may allow differences in glycemic regulation due to differences in insulin PK to be detected.

Additionally, the development of ultra-rapid insulins has the potential to further improve glycemic control achieved under closed loop by allowing the Bionic Pancreas to respond more efficiently to rising CGM glucose. Preliminary clinical studies of BC222 insulin lispro (Adocia) have shown increased insulin availability in the 30 minutes after a meal bolus and lower post-prandial glucose excursions, both via infusion pump or injections in type 1 and type 2 diabetes, when compared with insulin lispro (Humalog, Eli Lilly). This improved pharmacokinetic and pharmacodynamic profile of BC222 insulin lispro may provide superior glycemic control compared to both Humalog and Novolog, which may be of particular importance for those subjects who have altered absorption and clearance rates.

I. d. Fully Integrated Bionic Pancreas

We have designed, built, and tested our first-generation working prototype BP system, which we refer to as the iLet, and which consists of a dual-chamber autonomous infusion pump. The iLet has been built according to Class

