In addition to the iLet itself, the entire iLet BP system includes a glass insulin cartridge, a glass glucagon cartridge, pigtail adapters that connect the drug cartridges to infusion sets, and a self-monitored blood-glucose (SMBG) meter. The SMBG meter that we will use is the Contour Next One (Ascensia). This meter is the successor to the Contour Next SMBG meter (Bayer), which was found to be the most accurate meter assessed in all three blood-glucose ranges tested (< 70, from 70 to 179, and ≥ 180 mg/dl) in a comparative accuracy study involving 17 point-of-care glucose meters.

I. e. Rationale and Potential Benefits

It has generally been assumed that the PK characteristics of rapid-acting insulin analogs are equivalent. This has led to them being treated as a commodity by insurance companies, who generally have only one rapid-acting analog on formulary. However, it is clear from our data that in many individuals there are differences between the PK of insulin lispro and insulin aspart that are consistent across 3 different experiments on different days. If these differences in PK affect glycemic regulation, then better glycemic control may be achieved by identifying a preferred insulin analog for an individual. To determine this, we will test lispro and aspart in the context of the bionic pancreas. We will further examine the effect of PK differences on glycemic control using the experimental ultra-rapid BC222 insulin lispro in a third bionic pancreas study arm, without altering the default PK parameters. An uncontrolled Test Run period with 4 subjects using the iLet with BC222 lispro for three days will be completed prior to initiating outpatient use of BC222 lispro in the iLet to verify safety and feasibility. Data from this Test Run will be reviewed before the RCT period can begin.

II. Hypothesis and Specific Aims

We hypothesize that differences in the PK characteristics of rapid and ultra-rapid insulin analogs will lead to differences in glycemic outcomes when delivered by the *insulin-only* configuration of the bionic pancreas. Specifically, we predict that insulin analogs that have faster absorption (numerically lower T_{max} and/or $T_{1/2max}$) and insulin analogs that have faster clearance (numerically lower terminal half-life) will result in lower mean glucose and/or a lower percentage of time in the hypoglycemic range.

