Aim 1: To conduct a randomized, single-blinded, cross-over study testing the *insulin-only* bionic pancreas in a home-use setting in up to 30 adult subjects (≥ 18 years of age) with type 1 diabetes comparing two commercially available rapid acting insulin analogs, insulin lispro (Humalog, Lilly) and insulin aspart (Novolog, Novo Nordisk.) A final insulin-only bionic pancreas arm will use the experimental ultra-rapid insulin BC222 insulin lispro (BC Lispro, Adocia). The focus will be on determining which fast-acting insulin would be best for use in the iLet bionic pancreas system.

Up to 30 subjects will participate in three 7-day study arms using insulin lispro, insulin aspart, and BC222 lispro in the bionic pancreas in random order. The co-primary outcomes will be mean CGMG and fraction of time spent with CGMG <54 mg/dl with comparisons made between arms for individual participants. Secondary analyses will include time in glycemic ranges (<50 , <60 , <70 , $70-120$, $70-180$, >180 , >250 mg/dl), coefficient of variation, mean postprandial excursion (difference in CGMG from the time of meal announcement to the peak CGMG in the first 4 hours after the meal announcement) for both mixed meal challenges, number of symptomatic hypoglycemic events, grams of carbohydrate consumed to treat hypoglycemia, and TDD of insulin, between arms for individual subjects.

III. Subject Selection

III. a. Inclusion Criteria

1. Age ≥ 18 years and have had clinical type 1 diabetes for at least one year
2. Diabetes managed using an insulin pump for ≥ 6 months
3. Have used a CGM for at least one cumulative month over the last 12 months
4. Prescription medication regimen stable for > 1 month, including any adjunctive anti-diabetic medications (except for medications that will not affect the safety of the study and are not expected to affect any outcome of the study, in the judgment of the principal investigator)
5. Willing to remain within a 250-mile radius of MGH. No air travel will be allowed, and subjects will still be expected to follow the visit schedule as described.
6. Willing to wear one Dexcom CGM sensor, and one leur-lock compatible infusion set that must be replaced every other day
7. Have a mobile phone they will have access to at all times during the study for making contact with study staff

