 19. Electrically powered implants (e.g. cochlear implants, neurostimulators) that might be susceptible to RF interference

20. Unable to completely avoid acetaminophen for duration of study
21. Established history of allergy or severe reaction to adhesive or tape that must be used in the study
22. History of eating disorder within the last 2 years, such as anorexia, bulimia, or diabulenia or omission of insulin to manipulate weight
23. History of intentional, inappropriate administration of insulin leading to severe hypoglycemia requiring treatment
24. Any diagnosed allergy to insulin lispro or insulin aspart
25. Lives in or frequents areas with poor Verizon wireless network coverage (which would prevent study staff from contacting subjects)
26. Any factors that, in the opinion of the principal investigator would interfere with the safe completion of the study

III. c. Source of Subjects

Subjects will be primarily recruited from those who completed our previously conducted Multiplex Pharmacokinetic Study (HRC protocol number 2010P001005), measuring the individual PK profile of each subject for each of the three rapid acting insulins. We will recruit up to 15 subjects who exhibited an atypical PK profile, with the largest differences between the insulin lispro and insulin aspart in either Tmax, T½max, or terminal half-life. Additionally, we will recruit up to 15 subjects who did not have a significant difference in Tmax, T½max, or terminal half-life between insulin lispro and insulin aspart. Most of these subjects will have met similar inclusion criteria to the ones for this study in the past, so we anticipate that most of them will meet inclusion criteria. Subjects in the Test Run will not be required to have shown significant difference in their PK and will be recruited from our general clinic population. However, they may be included in the RCT period provided they meet these recruitment goals.

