 - < 70 mg/dl
 - 70-120 mg/dl
 - 70-180 mg/dl
 - >180 mg/dl
 - >250 mg/dl
- Within day coefficient of variation (CV)
- Mean postprandial excursion (difference in CGMG from the beginning of the meal challenge to the peak CGMG in the 4 hours after the meal) for both mixed meal challenges
- Number of symptomatic hypoglycemic events per day
- Grams of carbohydrate consumed to treat hypoglycemia per day
- TDD of insulin

VI. b. 3. Other Outcomes

- Mean number of meal announcements per day
- CGM Reliability index, calculated as percent of possible values actually recorded by CGM
- CGM MARD from Dexcom G5 CGM versus time-stamped BG values from meter downloads (any other BG values will not be considered)
- Percentage of days with mean CGM glucose < 154 mg/dl (estimated average glucose corresponding to

an A1c of 7%)

- Mean postprandial AUC (4 hours following each meal challenge) for both mixed meal challenges
- Mean number of daily BG measurements
- Number of severe hypoglycemic events (subject unable to self-treat, requiring the assistance of another person)
- Mean daily basal insulin dose
- Mean daily bolus insulin dose
- List of technical faults associated with the bionic pancreas including cause and resolution

The primary analysis of the designated endpoints will be calculated on an intention-to-treat basis. In cases where an arm was not completed we will use the available data from that arm in the data analysis. We will calculate percentages, means standard deviations (and medians and interquartile ranges as appropriate), and ranges in descriptive analyses. We will use paired t-test for comparison of means for normally distributed outcomes and the Wilcoxon Signed Rank test for comparisons of medians on non-normally distributed outcomes. In a secondary analysis we will look for any period effect and any interaction between treatment and period, although no such interaction is predicted and there is probably insufficient power to identify a small interaction. We may, in exploratory analyses, also stratify subjects for secondary analyses of the pre-specified endpoints by the following characteristics: sex, age, usual care insulin total daily dose, body mass index, baseline A1c, and use of CGM in usual care.

VI. c. Power Analysis

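### For lispro versus aspart, no planned analysis relates a participant's own PK to glycemia, although the rationale and the recruitment rest on that link

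*Combined protocol and SAP*

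**What the plan says.** **Question and purpose.** After reporting the earlier PK results, section I.c says: "What is not yet clear is whether these differences in PK would result in differences in glycemic regulation". Section I.e continues: "If these differences in PK affect glycemic regulation, then better glycemic control may be achieved by identifying a preferred insulin analog for an individual", and then "To determine this, we will test lispro and aspart in the context of the bionic pancreas". Section II opens: "We hypothesize that differences in the PK characteristics of rapid and ultra-rapid insulin analogs will lead to differences in glycemic outcomes", and predicts that analogs with faster absorption or clearance give lower mean glucose, less time in hypoglycemia, or both. Section VIII presents the trial as a step toward choosing insulin by a person's PK parameters.

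**Recruitment.** Section III.c says: "We will recruit up to 15 subjects who exhibited an atypical PK profile", meaning those with the largest lispro-aspart differences, plus up to 15 without a significant difference. People from outside the earlier PK study may be assigned to a PK group on other data or on anti-insulin antibody titer.

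**Aim 1.** Section II gives the focus as: "The focus will be on determining which fast-acting insulin would be best for use in the iLet bionic pancreas system".

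**Analysis.**
- VI.b plans comparisons within participants and three pairwise comparisons between arms.
- The methods paragraph after VI.b.3 gives paired t or Wilcoxon signed rank tests and a check for period effects and treatment-by-period interaction. In exploratory work the team may "also stratify subjects for secondary analyses of the pre-specified endpoints by the following characteristics: sex, age, usual care insulin total daily dose". Three more characteristics complete the list: CGM use, A1c at baseline and BMI.
- VI.c says autoregressive time series models will be used for comparisons within each subject.

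**The concern.** The variable that defines recruitment does not appear in the analysis. Followed exactly, the plan can say which insulin is better on average and which individuals differ between insulins. It cannot say whether those individuals are the ones whose PK predicted it, or whether the better insulin is the one their PK favored.

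Two consequences follow. First, the group lispro-aspart mean could show little even if PK drove each person's response, because many participants have no PK difference and the rest do not all point the same way. Second, any later statement that PK should guide the choice of insulin would rest on an analysis chosen after the outcomes were known.

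**Working it through.** **1. The plan's own figures.** The directional splits in I.c (favoring lispro + favoring aspart) are 6 + 1 = 7 for Tmax, 2 + 4 = 6 for T½max and 8 + 6 = 14 for terminal half-life, of 22. All match VI.c. VI.c gives no effect size, SD or power for this trial, so there is no power figure to reproduce.

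**2. What each planned analysis can answer.**
- Paired t or Wilcoxon tests between arms: the Aim 1 product question. PK is not used.
- Autoregressive comparison per participant: which individuals differ. No cancellation between participants, but no link to PK.
- Optional stratification: six characteristics, none of them PK group, Tmax, T½max or half-life.
- BC222: I.e says "We will further examine the effect of PK differences on glycemic control using the experimental ultra-rapid BC222 insulin lispro". This is a contrast between products and carries no information on an individual's lispro-aspart PK.

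**3. Why the group mean is a weak proxy.** Assume a benefit of 10 mg/dl on the insulin that a person's PK favors and zero for those without a difference. Let L and A be the numbers favoring lispro and aspart.
- Lost to dilution = 10 − 10 × (L + A)/22
- Lost to cancellation = 10 × (L + A)/22 − 10 × |L − A|/22
- Remaining group shift = 10 × |L − A|/22

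| PK measure | L, A, none | Lost to dilution | Lost to cancellation | Remaining shift |
|---|---|---|---|---|
| Half-life | 8, 6, 8 | 3.6 | 5.5 | 0.9 mg/dl |
| T½max | 2, 4, 16 | 7.3 | 1.8 | 0.9 mg/dl |
| Tmax | 6, 1, 15 | 6.8 | 0.9 | 2.3 mg/dl |

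Only for half-life is cancellation the main loss. For T½max and Tmax it is dilution.

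**4. Illustrative power.** Two-sided 0.05, each PK measure taken in turn as the only driver. The SD of paired differences is assumed: 10 × √(2(1 − r)), using the SD of 10 mg/dl that VI.c reports for the bionic pancreas arm of an earlier trial. An assumed r of 0.5 gives 10; r of 0.68 and 0 give 8 and 14. Simulation with 22 participants resampled from the counts gives:

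| | Half-life | T½max | Tmax |
|---|---|---|---|
| Group paired t, 10 mg/dl | 6.4% | 6.6% | 14.8% |
| Regression on PK sign, 10 mg/dl | 92% | 59% | 60% |
| Regression, 10 mg/dl, SD 14 to 8 | 68-99% | 35-76% | 36-77% |
| Group paired t, 5 mg/dl | 5.3% | 5.4% | 8.0% |
| Regression on PK sign, 5 mg/dl | 41% | 20% | 20% |

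Regression check with the counts held fixed: noncentrality = (10/10) × √Sxx, where Sxx = (L + A) − (L − A)²/22, on 20 df. Sxx is 13.82, 5.82 and 5.86; noncentrality is 3.72, 2.41 and 2.42; power is 94%, 63% and 64%.

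The two tests address different nulls, and the sign model is correct by construction, so the regression figures are a best case. An effect of 10 mg/dl is optimistic: VI.c reports 162 − 141 = 21 mg/dl for the bionic pancreas against usual care.

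**5. Choice after the fact.** Three PK measures by two co-primary outcomes give six candidate tests. None is in the plan; this is only what an unplanned analysis could draw on. At 0.05 each and under independence, the chance of at least one false positive is 1 − 0.95⁶ = 0.265, and lower if the tests are correlated.

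**The case against.** **The hypothesis is about analogs, not individuals.** A reader might infer that the stated hypothesis itself concerns a participant's own PK. Section II does not say so: its wording is at analog level, and Aim 1 asks which insulin suits the iLet, which the planned tests answer. This stands. The individual question comes from I.c, I.e, III.c and VIII, and the hypothesis shares the PK-to-glycemia link. Aim 1 alone would not need recruitment by PK.

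**The plan already has individual comparisons.** A reader might also infer that the plan would miss a PK-driven response altogether. It would not: the autoregressive models could show significant differences in both directions. The power figures concern only the group paired test. What is missing is the step that sets the individual results against PK.

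**The illustration rests on assumptions.** Effect, SD and single driver are assumed. The 22-person mix is not the planned split of up to 15 and up to 15. Participants below the cut-offs in I.c are coded as exactly zero. All of this stands, so the figures are not a design calculation. The gap is in the text and does not depend on them.

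**The trial is exploratory.** VI.c uses this to explain the absent power analysis. It does not explain listing six stratifiers and leaving out the one that defines recruitment.

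**Conclusion.** The point holds for lispro versus aspart. Rationale, recruitment and intended use ask whether individual PK predicts the better insulin, and nothing in section VI tests or describes that relation. This should be fixed before outcome data are seen. It does not affect the validity of the Aim 1 comparisons.

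The size is known only by illustration. Under the assumptions in the working, the group test has about 6% to 15% power to register a 10 mg/dl PK-driven effect, against 59% to 92% for a PK-sign regression. Because the nulls differ, the gap between these figures should not be read as power lost by the plan. Nor do the documents support reading the weakness as cancellation throughout; that applies mainly to half-life.

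**What to change.** In VI.b, pre-specify one PK-linked lispro-aspart analysis, labelled exploratory.

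- **Model.** For example, regress each participant's lispro-minus-aspart difference in mean CGMG on the measured lispro-minus-aspart PK difference. The prediction in section II implies a positive slope. Use a rank or permutation version for time below 54 mg/dl, which is likely to be small and skewed. A PK-group-by-insulin analysis would also close the gap.
- **PK measures.** Name one lead measure before outcomes are seen. Treat the others as supportive and analyze each on its own signed difference, so that participants whose measures disagree need no composite direction.
- **Population.** Restrict to participants with measured PK. Report those classified by antibody titer separately: III.c ties high titers to slow analog PK, which gives no lispro-versus-aspart direction.
- **Description.** Add PK group to the exploratory stratifiers, and tabulate the individual autoregressive results by PK-favored insulin. The table cannot carry a test: a two-sided sign test at 0.05 needs 12 of 14 concordant for half-life (p = 0.013; 11 of 14 gives 0.057), 7 of 7 for Tmax and 6 of 6 for T½max.
- **Keep** the existing paired tests for Aim 1 and for BC222.

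The cost is SAP wording, one model and one table, mostly on PK data already held. The limit is numbers. At most about 22 people contribute (I.c gives both 20 and 22 for the earlier study), plus any with PK data from another source. Of a full 30, at least 30 − 22 = 8 would come from outside that study. At 5 mg/dl the sign regression has about 20% power for Tmax or T½max, and about 15% if only 15 of the 22 join. Power for the continuous PK difference cannot be computed from the documents.

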- Usage of CGM (type of CGM, days per month worn, usage of data, whether insulin is dosed based on CGM alone, alarm settings)
- Height and weight
- Blood pressure
- EKG if applicable
- Hemoglobin A1c
- Anti-insulin antibody titers
- Plasma, for future insulin antibody assays
- Urine HCG (pre-menopausal females)
- eGFR

VI. a. 2. All Study Arms (including the Test Run period):

- CGMG (CGM glucose) every five minutes from the Dexcom CGM
- All fingerstick BG measurements taken by the subject (meter download)
- Insulin total daily dose from bionic pancreas download
- Timing of meal announcements and size of meals announced from bionic pancreas download

- Day, time, fingerstick BG measurements, CGMG readings, and insulin doses from each meal challenge
- Time subjects were not under bionic pancreas control
- List of technical faults associated with the bionic pancreas including cause and resolution
- Body weight after each study arm
- Anti-insulin antibody titers and plasma after each study arm
- Date of last menstrual period
- Information collected from the daily email survey and phone calls including but not limited to hypoglycemia, carbohydrate interventions, any nausea and/or vomiting, any other adverse events, time spent exercising each day, exercise intensity, and exercise exposure (time X intensity), any unscheduled infusion set changes or Dexcom CGM sensor changes, and alcohol intake.
- Data from questionnaires about attitudes and expectations regarding the bionic pancreas at baseline and on day 7 of each arm (RCT portion the study only).

VI. b. Study Endpoints

Statistical comparisons will be made between insulin analogs within a single participant. Three pairwise comparisons will be made between arms.

Data from the uncontrolled Test Run period will be reviewed to verify safety before proceeding with the RCT portion of the study. Descriptive statistics will be compiled based on the same analyses planned for the RCT portion of the study but no formal statistical analyses will be done. This period has no control and is intended to verify the iLet with BC222 lispro is safe and operating as expected prior to initiating outpatient experiments in a larger cohort.

VI. b. 1. Co-Primary endpoint analyses

The co-primary outcomes will be mean CGMG and fraction of time spent with CGMG <54 mg/dl.

VI. b. 2. Secondary endpoint analyses

Secondary analyses will include:

- Fraction of time spent within each of the following ranges:
 - < 50 mg/dl
 - < 60 mg/dl

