As this study is exploratory in nature, no formal power analysis has been performed. From our insulin specific data collected in our previous study, we identified 7 out of 22 had a difference in t_{max} , 6 out of 22 had a difference in $t_{1/2max}$ and 14 out of 22 had a difference in terminal half-life. We'd like to recruit all 22 of these subjects to participate in this study. Given the occurrence rate of different PK profiles, we believe this will still capture significant information. The sample size of 4 for the Test Run period is a convenience sample with no statistical implications.

We previously showed in a multicenter, outpatient, random-order crossover trial (n=39, 11 days each arm) that the bionic pancreas (BP) reduced group mean CGM glucose (141 ± 10 vs. 162 ± 29 mg/dl, $p < 0.0001$) and percent of time spent <60 mg/dl (0.6 ± 0.6 vs. $1.9 \pm 1.7\%$, $p < 0.0001$) relative to usual care (UC) with pump \pm CGM (El-Khatib FH, et al. Lancet. 2017; 389:369–80). We applied a statistical approach to these data that we will use in this study for comparisons within subjects to determine how many individuals saw benefit for each outcome. We compared the average CGM glucose and average time <60 mg/dl between the BP and UC arms for each patient using autoregressive time series models to determine significance of differences. We found that 72% of subjects had a statistically significant reduction in mean CGM glucose, 51% had significant reduction in time <60 mg/dl, 44% had a significant reduction in both, and 97% had a significant reduction in at least one outcome. These analyses provide a new prospective on the efficacy of the BP emphasizing the benefit to individuals rather than the group as a whole. Subjects least likely to benefit were those who had extremely tight glycemic control and minimal hypoglycemia under UC.

VII. Risks and Discomforts

Subjects may experience mild discomfort associated with the insertion of the infusion set and the Dexcom sensor into the SC tissues. This is expected to be the same as their usual care.

There is a risk of hypoglycemia. This risk is expected to be less than the risk during the subjects' lives outside the trial based on data from earlier trials. All of our previous studies have shown that hypoglycemia is significantly reduced in all configurations of the bionic pancreas when compared with usual care. Based on our experience,

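### Within-participant significance tests used to count who benefits cannot separate insulin from week, because each participant has each insulin in only one 7-day arm

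*Combined protocol and SAP*

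**What the plan says.** Under Aim 1 (Section II), up to 30 participants "participate in three 7-day study arms using insulin lispro, insulin aspart, and BC222 lispro" in random order. The co-primary outcomes are mean CGM glucose and the fraction of time below 54 mg/dl, "with comparisons made between arms for individual participants". Section VI.b repeats the level of comparison: "Statistical comparisons will be made between insulin analogs within a single participant. Three pairwise comparisons will be made between arms".

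Section VI.c names the individual-level method. It refers to "a statistical approach to these data that we will use in this study for comparisons within subjects to determine how many individuals saw benefit", and says the earlier trial's arms were compared for each patient "using autoregressive time series models to determine significance of differences". Results from that trial (n=39) illustrate the method: 72% had a significant reduction in mean CGM glucose, 51% in time below 60 mg/dl, "44% had a significant reduction in both, and 97% had a significant reduction in at least one outcome".

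The methods paragraph that closes VI.b.3 instead gives paired t-tests or Wilcoxon signed rank tests, on an intention-to-treat basis. It adds: "In a secondary analysis we will look for any period effect and any interaction between treatment and period".

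At the change of arm (V.d.v) the device memory is wiped, the controller is re-initialised, and a new CGM sensor is in place. Diet and exercise are unrestricted, with a request to keep habits similar (V.d.iii).

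**The concern.** A person's mean glucose can differ between two weeks on the same insulin because of sensor, activity, diet, illness or how the controller adapts after its restart. An autoregressive model handles correlation between readings inside a week. It cannot estimate a shift that lasts the whole week, because one person's data contain no second week on the same insulin.

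At stake is the meaning of the individual count. Section VIII presents the trial as a step towards prescribing insulin individually by PK profile. A reader would take the number of participants with a significant difference as the number who have a better insulin. Part of that number may be week-to-week variation, and the plan attaches no such caution to it.

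A second issue is which analysis carries the co-primaries. Aim 1 and VI.b point to individual comparisons, while the methods paragraph points to paired tests across participants.

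**Working it through.** **No design figure to reproduce.** VI.c states that no formal power analysis was done, and no alpha or error rate is given for the individual test. The one figure that can be checked is the worked example (step 5).

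**1. Degrees of freedom.** Three insulins in three weeks give one week per insulin, so there are 0 degrees of freedom for week-to-week variance within a person. The two meal challenges fall inside the same arm and do not replicate the week.

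**2. False-positive rate for mean CGM glucose, no insulin effect.** Assumptions: two-sided alpha 0.05; k = week SD ÷ model standard error of one arm mean. The true variance of an arm mean is (1 + k²) times the variance the model sees, so

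rate per pair = 2 × [1 − Φ(1.96 / √(1 + k²))].

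| k | 1.96/√(1+k²) | Rate per pair | Excess over 5% | One direction | Expected of 30, one direction |
|---|---|---|---|---|---|
| 0 | 1.960 | 5.0% | 0 | 2.5% | 0.75 |
| 0.25 | 1.901 | 5.7% | 0.7 points | 2.9% | 0.86 |
| 0.5 | 1.753 | 8.0% | 3.0 points | 4.0% | 1.19 |
| 1 | 1.386 | 16.6% | 11.6 points | 8.3% | 2.49 |

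The row k = 0 is ordinary test error. Aliasing adds 0.11, 0.44 and 1.74 expected participants in the other rows (0.86, 1.19 and 2.49, each minus 0.75).

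**3. What k might mean in mg/dl.** This is illustration only. Readings every 5 minutes (VI.a.2) give 7 × 288 = 2,016 per arm. With an assumed CGM SD of 40 to 50 mg/dl and an assumed autocorrelation time of 60 to 180 minutes, the model standard error of an arm mean is 4.37 to 9.45 mg/dl. An assumed week SD of 5 mg/dl then gives k of 1.14 down to 0.53, and a rate per pair of about 20% down to 8%. None of these inputs except the sampling interval is in the documents.

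**4. Time below 54 mg/dl.** VI.c reports 0.6% of time below 60 mg/dl on the earlier bionic pancreas; 0.006 × 2,016 ≈ 12 readings per week, and readings below 54 cannot be more frequent. In a null simulation of the AR(1) mean test, assuming 1 to 3 low episodes per week averaging 15 to 25 minutes and no week variation, the one-direction rate was about 0 to 0.5%, well below 2.5%. The table in step 2 therefore does not apply to this outcome.

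**5. Worked example in VI.c.** At least one = first + second − both = 72 + 51 − 44 = 79%. Rounding can raise this only to 72.5 + 51.5 − 43.5 = 80.5%. With n=39 the only whole numbers matching 72%, 51% and 44% are 28, 20 and 17, giving 28 + 20 − 17 = 31 of 39 (79%). The stated 97% would need 38 of 39.

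**6. The paired tests.** Each participant's week shifts enter the between-participant spread of paired differences, so the group test's error term includes them. In simulation with n=22 and n=30, and k of 0, 0.5 and 1, the paired t-test kept an error rate of 5%.

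**The case against.** The study calls itself exploratory, Aim 1 focuses on which insulin is best for the device, and the autoregressive method appears only in VI.c. The group tests that would answer the Aim 1 question are already planned. Random order, automated control, similar habits and a period analysis all help. The size of the problem is unknown, and at a ratio of 0 it vanishes.

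Most of this stands as a limit on size and reach. It does not remove the aliasing: random order protects the group average, the period analysis addresses an average period effect, and automation reduces noise without supplying a second week. VI.c uses the word exploratory to explain the missing power analysis, not to limit individual claims.

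Some stronger readings are tempting but unsupported:

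- A reader might infer that the trial cannot compare the insulins. Step 6 shows that the paired comparison is sound.
- A reader might take the 53% chance of at least one false benefit among 30, which is 1 − (1 − 0.025)^30 at ratio 0, as evidence of aliasing. It is ordinary multiplicity.
- A reader might say that the plan has no reference group. Section III.c recruits up to 15 participants without a significant PK difference beside up to 15 with one; what is missing is a stated analysis of that contrast.
- From "14 out of 22 had a difference in terminal half-life" a reader might conclude that at most eight (22 − 14) could join the same-PK group from the earlier cohort. Section I.c counts differences above 50%, whereas III.c refers to a significant difference, so eight is not an established ceiling.

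**Conclusion.** The concern holds for the individual significance tests and the count built on them. That insulin and week cannot be separated within a person follows directly from the design and needs no assumption. The amount of inflation does: for mean CGM glucose the rate per pair runs from 5.0% to 16.6% as the week SD goes from 0 to 1 times the model standard error, at an assumed two-sided alpha of 0.05. The documents do not show where in that range the trial lies. For time below 54 mg/dl no comparable rate can be given, and a normal-theory test may run well below its nominal level.

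The role of each analysis for the co-primaries is unclear and needs stating. The 97% in VI.c cannot be reconciled with the other three percentages; this is a separate, smaller correction that changes no planned test.

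**What to change.** 1. In VI.b, state that conclusions about insulin differences rest on the across-participant paired comparison already planned, and that the individual autoregressive analysis is descriptive.
2. Report each participant's arm estimates and pairwise differences with intervals, labelled insulin-plus-week differences. Do not call a significant individual result a demonstrated insulin benefit.
3. If counts are kept, give them per named pair, outcome and direction at a stated alpha. For mean CGM glucose only, print the nominal chance count beside each (0.025 × 30 = 0.75 for one direction at two-sided 0.05) and note that it omits week variation. For time below 54 mg/dl, print no normal-theory benchmark.
4. Correct or explain the 97% in VI.c.

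A comparison of counts between the different-PK and same-PK groups is optional and should be descriptive.

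The cost is SAP wording, with no new visits or data. The downside is weaker individual-level claims. Measuring week-to-week variance within a person would need repeated weeks on the same insulin, which reanalysis cannot supply.
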